## 8.7. Analysis of Safety

## 8.7.1. Dose-Limiting Toxicity (DLT)

The primary endpoint is based on the incidence of DLT at each dose cohort and the overall safety profile of WT2725 Dosing Emulsion. The incidence of DLT will be evaluated during the DLT Evaluation Period, which extends from the day of the first dose to just prior to the fifth dose of study drug (Days 1 to 29). No more than 4 doses of study drug will be administered during the DLT Evaluation Period.

DLTs are defined as any Grade 3 or greater AE that occurs after the administration of study drug during the DLT Evaluation Period that are not related to underlying disease, intercurrent illness, or concomitant medications. (Changes in hematology parameters need to have been confirmed on repeat assessment and constitute at least a 2 grade shift. Grade 3 AEs of nausea, vomiting, and fatigue that are common and manageable in cancer patients will not be considered DLT if they can be ameliorated to < Grade 3 with standard supportive care management.) AEs will be graded according to the CTCAE.

The number and percentage of patients will be presented for DLT and non-DLT by each dose cohort during the DLT evaluation period. Specific DLTs are flagged in the collection of AE data and will be listed.

The number and percentage of DLT events will be presented by dose cohort and for all patients. The DLTs observed for the DLT evaluation period will be summarized by dose cohort and for all subjects by MedDRA SOC and PT. DLTs will also be summarized by category of NCI CTCAE grade.

#### 8.7.2. Adverse Events

All AE tables summarized by MedDRA coding will be sorted alphabetically by SOC and decreasing incidence of preferred term within based on the total number of patients. AE summaries will be produced by dose cohort and tumor group.

Treatment-emergent adverse events (TEAEs) will be defined as:

- AEs that occurred on or after the first dose of study drug and on or before the 30th day after the last dose of study drug,
- AEs with a missing start date and a stop date on or after the first dose of study drug, or
- AEs with both a missing start and stop date.

All the following summaries of AEs, unless otherwise stated, will include only TEAEs. An overall summary of AEs, including the number and percentage of patients reporting at least 1 AE, treatment-related AEs, AEs with an outcome of death (defined as CTCAE Grade 5 or outcome is "fatal"), serious AE (SAE)s, treatment-related SAEs, and AEs leading to treatment discontinuation (defined as an event with an outcome code of "drug withdrawn").

Tables will present the number and percentage of AEs by starting dose cohort and overall and by MedDRA SOC and PT for the Safety population. The following tables will be produced:

- TEAEs (including number of events and patient incidence)
- Treatment-Related TEAEs. "Related" is defined as all responses other than "Unrelated" from the CRF. If a patient reports more than one AE within the same treatment regimen, SOC and PT, and any are related, it will be summarized as related. If in CRF, no choice is ticked, it will be treated as "Related".
- SAEs
- Treatment-Related SAEs
- TEAEs by maximum CTCAE Grade
- TEAEs leading to treatment discontinuation
- TEAEs with outcome of death

Similar tables will also be presented by the last dose received before the start of the event. For this summary, column headers will need to include all patients who were ever dosed at that dose level. Additionally, patients may be counted more than once for each event as the events will be tabled by the last dose level received on or prior to the start date of the event.

Listings of all TEAE, AE with outcome of death, SAEs, and AEs leading to discontinuation will be presented. A separate listing for non-treatment-emergent AEs will also be provided.

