4. AMENDMENT NO. 2, PROTOCOL VERSION 3.0 (13 JUL 2012)

The following changes were made to the protocol in order to adhere to the sponsor's internal standards:

- Revise definitions for reporting adverse events:
 - remove “unlikely” from the reasons for causal relationship of adverse events to study medication and adjust adverse event statistical analysis accordingly
- Change start time for collection of adverse events, serious adverse events, and pregnancies to the time of informed consent

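### SAP 8.7.2 defines treatment-emergent AEs by onset date with no worsening clause, so a screening-onset AE that worsens on treatment can be missing from the AE tables

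*SAP*

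**What the plan says.** SAP 8.7.2 gives three ways for an AE to be treatment-emergent:

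1. "AEs that occurred on or after the first dose of study drug and on or before the" 30th day after the last dose;
2. "AEs with a missing start date and a stop date on or after the first dose of study drug";
3. "AEs with both a missing start and stop date".

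The definition then controls the tables: "All the following summaries of AEs, unless otherwise stated, will include only TEAEs". These are the overall summary and the tables of TEAEs, related TEAEs, SAEs, related SAEs, maximum CTCAE grade, events leading to discontinuation, and deaths. A parallel set is produced by dose level, for which "the events will be tabled by the last dose level received on or prior to the start date of the event". Events outside the definition go to a listing: "A separate listing for non-treatment-emergent AEs will also be provided".

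On collection, Protocol Amendment No. 2 records this change: "Change start time for collection of adverse events, serious adverse events, and pregnancies to the time of informed consent". Amendment No. 6 puts screening at 21 days.

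DLTs are defined separately in SAP 8.7.1 as "any Grade 3 or greater AE that occurs after the administration of study drug during the DLT Evaluation Period", subject to attribution and supportive-care conditions. Changes in hematology values must also amount to at least a 2-grade shift.

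**The concern.** Safety and tolerability is a primary objective (SAP 3.1), and the occurrence of AEs is part of the primary endpoint (SAP 6.2). The tables in 8.7.2 are where the reader will see how often events, related events and severe events happened on WT2725.

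Collection starts before dosing, so the database can hold AEs with a pre-dose onset that are still ongoing at the first dose. If one of them becomes more severe or serious on treatment, that change is on-treatment safety information. A definition tied to onset has no place for it. There is a concrete route in this trial: the schedules (SAP Tables 1 and 3) place a DTH skin test injection on Day -2, and the test uses the WT2725 peptide (SAP 6.3). If a reaction to it were reported as an AE and worsened after the Day 1 dose, its onset would precede the first dose.

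At stake is an undercount in the main AE tables, in cohorts so small that one event is visible.

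**Working it through.** There is no plan figure to reproduce. The check applies the rules to cases.

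**Step 1. What *occurred* means in rule 1.** The SAP does not say outright. Two features of 8.7.2 point to onset: rule 2 is needed only if the start date is what rule 1 tests, and the by-dose tables assign an event by its start date.

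**Step 2. Apply the three rules.** Each case is an AE that begins between consent and first dose and is ongoing at first dose.

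| Case | Rule 1 | Rule 2 | Rule 3 | Result as written |
|---|---|---|---|---|
| A. Known onset, Grade 1; reaches Grade 3 after Day 29, inside the TEAE window; one record | Fails: onset before dosing | Fails: start date known | Fails: start date known | Not a TEAE; in no 8.7.2 table |
| B. As A, but reaches Grade 3 during Days 1 to 29 | Fails | Fails | Fails | Not a TEAE; may be in the 8.7.1 DLT tables |
| C. Day of onset missing; month and year are those of the first dose | Passes: SAP 7.3 sets the start to the first dose date | n/a | n/a | TEAE, worsened or not |
| D. As A, but the grade increase is entered as a new AE with its own start date | Passes | n/a | n/a | TEAE |

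Case A is the gap. It also cannot be placed in the by-dose tables, because no dose precedes its start date. In case B, if *occurs* in the DLT definition is read as reaching Grade 3, the same event can be a DLT and yet be absent from the maximum-grade TEAE table.

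**Step 3. Look for a worsening rule elsewhere.** SAP 7.3 covers date imputation only. SAP 8.7.1 has the 2-grade hematology shift, for DLT only. SAP 8.7.3.5 has a baseline-to-maximum grade shift table, for laboratory values only. None changes the TEAE flag.

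**Step 4. Scale, as illustration only.** The documents give no rate for such events. Assume one patient in a cohort has a case A event and nobody else has a Grade 3 or higher TEAE. The sizes are 6 (the most in an escalation cohort) and 10 (the approximate Part 2 cohort). Wilson 95% limits are [2np + z² ± z√(z² + 4npq)] / [2(n + z²)], with z = 1.96 and z² = 3.84.

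- 0/6: upper limit 3.84/9.84 = 39.0%; interval 0 to 39.0%.
- 1/6 = 16.7%: (5.84 ± 1.96√7.17)/19.68 = (5.84 ± 5.25)/19.68; interval 3.0 to 56.4%.
- 0/10: upper limit 3.84/13.84 = 27.8%; interval 0 to 27.8%.
- 1/10 = 10%: (5.84 ± 1.96√7.44)/27.68 = (5.84 ± 5.35)/27.68; interval 1.8 to 40.4%.

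The SAP plans Wilson intervals for best overall response, not for AE rates. They are used here only to show what one event means at these sizes.

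**The case against.** The strongest objection is that the deciding fact is not in view. SAP section 2 says the plan is to be read with protocol version 7 and the CRF, and the supplied protocol file is an amendment history without the AE section. If sites enter a grade increase as a new AE, case D applies and rule 1 already captures it. This stands, and it makes the conclusion conditional. It does not remove the point: the SAP neither states that convention nor refers to it.

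Second, a reader might infer that the gap covers the many symptoms patients with advanced cancer have at entry. The documents do not support that. Medical history is collected at screening and summarised separately (SAP 8.4), so a symptom present at consent may be history rather than an AE. The exposed group is narrower: AEs that begin after consent, are ongoing at first dose, and then worsen.

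Third, a reader might infer that such events disappear. They do not. The non-TEAE listing holds them, DLTs are tabulated under 8.7.1 without the TEAE restriction, laboratory worsening appears in the shift tables, and QTc, vital signs and weight have change-from-baseline summaries. This stands for those categories. A symptomatic AE that worsens outside the DLT definition is left with a listing only.

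Fourth, the definition does not exclude every pre-dose AE. Missing and partial start dates can bring one in (case C), so it is inexact to say that only events starting on or after the first dose are counted. This stands too. It also leaves an odd result: an AE of uncertain onset is counted, and one with documented pre-dose onset and documented worsening is not.

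**Conclusion.** The point holds in conditional form. As written, SAP 8.7.2 classifies by onset date or missing dates and has no worsening clause. An AE with a known onset between consent and first dose that increases in grade or becomes serious on treatment is left out of all the 8.7.2 tables, unless the change is recorded as a separate AE.

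This rests on two assumptions: *occurred* means onset, which the rest of 8.7.2 supports, and grade increases are kept on the original record, which the supplied documents neither confirm nor rule out.

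The number of patients affected cannot be estimated. For these AEs the direction is certain, since omission can only lower TEAE counts. A reader might go further and infer that AE rates as a whole are biased downward. That is not shown, because the missing-date rules can add screening events to the tables.

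A reader might also infer that dose escalation or the MTD is compromised. The documents do not support that: escalation counts DLTs (SAP 4.1.1), and MTD determination uses DLT incidence and the overall safety profile (SAP 6.2). The TEAE flag enters neither the DLT definition nor the escalation rule. The weakness is in the reporting of a primary safety component. It should be corrected before the tables are programmed.

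**What to change.** Add a fourth TEAE rule to SAP 8.7.2: *AEs with onset before the first dose that increase in CTCAE grade, or become serious, from the first dose through the 30th day after the last dose.* Add two handling rules: tabulate such events at the post-dose grade, and use the date of worsening in place of the start date in the by-dose tables. State that *occurred* in rule 1 means onset.

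Check how the CRF records a change in grade or seriousness. If each change is a new dated record, say so in 8.7.2; the fourth rule then serves as a safeguard, and the programming must avoid counting the same worsening twice.

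The cost is one rule and one derived flag. The downside is data: if the CRF keeps a maximum grade without its date, the affected records need a query. Where the date cannot be recovered, count the event as treatment-emergent and footnote it. That may include a few AEs that had already peaked before dosing, a small overcount in the cautious direction.

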#### 4. STUDY DESIGN

# 4.1. General Description

This is a Phase 1, open-label, dose-escalation, 2-part study in adult patients with advanced malignancies known to overexpress the WT1 protein. The study will primarily evaluate DLT and define the MTD of WT2725 Dosing Emulsion during the DLT Evaluation Period, which extends from the day of the first dose of study drug to just prior to the fifth dose (Days 1 - 29). In addition, antitumor activity and biomarkers indicative of immune response will be evaluated from the first dose until discontinuation of the patient from the study. An end of study assessment will take place within 28 days after the last dose of study drug and prior to the start of alternate antineoplastic therapy.

The initial patients in each dose escalation cohort will be enrolled at least one week apart to evaluate initial safety from the first 2 patients, then a "rolling-six" design will be employed that allows accrual of 2 to 6 patients concurrently in each dose escalation cohort.

In Part 1 of the study, the 0.3 mg cohort will be conducted first. After safety and tolerability have been established for the first cohort, enrollment of subsequent patients will be conducted sequentially in subsequent cohorts and continue until the MTD or all planned cohorts are attained. Enrollment of each cohort may include patients with any of the eligible tumor types (see below). Enrollment of the highest tolerable dose cohort (MTD or highest planned cohort) will continue until there are at least 6 patients total in the study with each tumor type that are evaluable for DLT, biomarkers, and response. This dose is considered the recommended phase 2 dose (RP2D). Enrollment of up to 3 RP2D cohorts of 10 patients each of a specific tumor type may take place at this dose in order to further characterize the safety and efficacy of WT2725 Dosing Emulsion at this

dose in these subsets of patients. Additional dose escalation cohorts after the initial expansion cohorts may be enrolled if a MTD has not been determined and significant signs of toxicity have not been observed in the expansion cohorts.

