#### Part 1:

[figure not shown]
- Vaccine Induction Phase: once every 7 days for 4 weeks (doses 1 5)
- Consolidation Phase: once every 14 days for 6 weeks (doses 6 9)
- Maintenance Phase: once every 28 days until discontinuation (dose 10 and thereafter)

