Hematology/ serum chemistry f	X c	X c	X c		X c		X c		X	
Urinalysis	X c	X c	X c		X c		X c		X	
12-lead ECG		X c			X c		X c		X	
DTH skin test injection				$X^g$	$X^{g,h}$			X g		
DTH skin test evaluation					X i	X j			X j	
Blood sample for CTL	X c	X c	X c		X c		X c		X	

<sup>s Tumor markers drawn from peripheral blood samples should be assessed at least every 4 weeks after the 1st dose but may be performed more frequently (For other tumor assessments, perform every 8 weeks after 1st dose or more frequently as clinically indicated).

Table 2: Schedule of Assessments for Consolidation Phase, Maintenance Phase, and End of Study – Part 1 (Continued)

	Consolidati	ion Phase a,b					Maintenanc e Phase a,b	End of Study	y b	Follow-up
	6 th dose	7 th dose	8 th dose		9 th dose					
	Day 43 (±2)	Day 57 (±2)	Day 71 (±2)	Day 83	Day 85 (±2)	Day 87	every 28 (+7) days	48 hours before End of Study Visit	within 28 days after last dose	every 3 months
Blood sample for Anti- WT1 antibody		X c			X c		X c,k		X	
Blood sample for retrospective biomarker analyses		X c			X c		X c,k		X	
Blood sample for PBMC isolation									X	
IHC tumor samples									X¹	
Tumor assessment		X c,m			X c,n		X c,m		X m	
Adverse events							•	•	•	
Concomitant medications										
Disease Progression/ Survival				107.000					Xº	Xº

Abbreviations: AML = acute myeloid leukemia, CA-125 = cancer antigen 125, CTL = cytotoxic T lymphocyte induction activity, DTH = delayed-type hypersensitivity reactivity, ECG = electrocardiogram, ECOG = Eastern Cooperative Oncology Group, FSH = follicle-stimulating hormone, HLA = human leukocyte antigen, IHC = immunohistochemistry, irRC = immune-related response criteria, IWG = International Working Group response criteria in acute myeloid leukemia, MRI = magnetic resonance imaging, PBMC = peripheral blood mononuclear cell, PET = positron-emission tomography, RT-PCR = reverse transcriptase-polymerase chain reaction, SPECT = single-photon emission computed tomography, WT1 = Wilms' tumor gene product 1

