- a Additional dosing windows are provided for patients who may need to recover from intercurrent medical conditions (see Section 8.3.2.1 of protocol).
- b All patients should complete an End of Study visit within 28 days after the last dose of study drug and prior to the start of alternate antineoplastic therapy.
- c Prior to study drug administration.
- d Includes systolic and diastolic blood pressures, pulse, respirations rate, and oral body temperature.
- e For females of child-bearing potential.
- f See Appendix IV of protocol for list of required laboratory tests at each visit.
- g Perform DTH skin test injections approximately 48 hours (but no sooner than 24 hours) prior to the evaluation.
- h Perform DTH skin test injections immediately before administration of study drug.
-  Evaluation should be made on the planned dosing day, prior to study drug administration.
- j Evaluation should be approximately 48 hours (but no sooner than 24 hours) after the DTH skin test injection.
- k Perform every 2nd dosing day starting after the 9th dose.
- Biopsy for tumor tissue samples after the last dose of study drug is not mandatory. Tumor samples will be obtained from all patients who provide consent. IHC need not be performed for patients with AML provided RT-PCR for WT1 transcript is assessed.

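### The TEAE window closes 30 days after the last dose, but a maintenance dose may be given up to day 35, so a new AE on days 31-35 is tabulated only if that dose is given

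*SAP*

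**What the plan says.** SAP section 8.7.2 defines treatment-emergent AEs (TEAEs) as those starting on or after the first dose and "on or before the 30 th day after the last dose of study drug", plus certain events with missing dates. It then sets the scope of the tables: "All the following summaries of AEs, unless otherwise stated, will include only TEAEs". None of the tables that follow states an exception. One is titled "TEAEs leading to treatment discontinuation". The two SAE tables lack the TEAE prefix in their titles, but nothing exempts them from the rule.

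Maintenance dosing is open-ended. SAP section 4.1 gives for Part 1: "Maintenance Phase: once every 28 days until discontinuation (dose 10 and thereafter". Part 2 has the same interval from dose 16. The maintenance columns of Tables 2 and 4 add a tolerance: "every 28 (+7) days". A footnote to the schedules adds: "Additional dosing windows are provided for patients who may need to recover from intercurrent medical conditions".

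On the closing visit, section 4.1 says: "An end of study assessment will take place within 28 days after the last dose of study drug".

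On visibility, section 8.7.2 says: "Listings of all TEAE, AE with outcome of death, SAEs, and AEs leading to discontinuation will be presented". It also provides a separate listing of AEs that are not treatment-emergent.

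**The concern.** The window is anchored on the last dose, and which dose is last depends on what happens next. If a permitted dosing interval is longer than the window, two patients with the same AE on the same day can be classified differently because one received another dose and the other did not. When the AE itself is the reason for stopping, the classification depends on the outcome that the table is meant to count.

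Safety and tolerability is a primary objective (section 3.1), and AEs are among the primary endpoint variables (section 6.2). Under section 4.1.3.2, patients may move to a higher dose once they have completed consolidation, so maintenance is where escalated doses are given. The tables by last dose received, which attribute events to those doses, carry the same TEAE restriction.

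**Working it through.** The plan gives no figure to reproduce; the check is day counting, with the most recent dose as day 0.

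**Inputs.** TEAE cut-off: day 30 (section 8.7.2). Maintenance interval: 28 days with a tolerance of +7 (Tables 2 and 4). Induction visits: 7 days apart, tolerance -1 day (Tables 1 and 3). Consolidation visits: 14 days apart, tolerance ±2 days (Tables 2 and 4). Part 2 cohort size: about 10 (section 4.1).

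**Longest routine gap between doses, by phase**

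| Phase | Longest gap | Within day 30? |
|---|---|---|
| Induction | 7 + 1 = 8 days | yes |
| Consolidation | 14 + 2 + 2 = 18 days | yes |
| Before a maintenance dose | 28 + 7 = 35 days | no |

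**Uncovered days.** 35 - 30 = 5 days, namely days 31-35. The permitted maintenance dosing days are 28 to 35, which is 8 days, and 5 of the 8 lie beyond the cut-off. As a share of the longest routine interval, 5/35 = 14% of days. If every dose is given on day 28, 29 or 30, nothing is uncovered.

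**The same event under two outcomes.** The dose is pending and a new AE starts on day 33.
- The next dose is given on day 35. The last dose is now later than the AE, so the AE is a TEAE and enters the tables.
- The AE ends treatment. Day 0 remains the last dose and 33 > 30, so the AE is not a TEAE and enters no AE table, including the discontinuation table. It appears only in listings.

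**Size in a rate.** With about 10 patients in a Part 2 cohort, one omitted event changes a cohort percentage by 1/10 = 10 percentage points.

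**Gaps outside the routine schedule.** The recovery windows could lengthen the wait, but their length is in a protocol section that is not in the text available. Footnotes to Tables 3 and 4 also let Part 2 patients who cut short the extended induction or consolidation resume on Day 71 or Day 169 at the discretion of the investigator and sponsor. A patient who misses only dose 15 could wait from Day 127 to Day 169, which is 42 days. These cases are not in the sizes above, but the same rule would apply to them.

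**End of Study timing.** If treatment is stopped on days 29-35, a visit no later than 28 days after the last dose can no longer take place, although the schedule still permitted a dose on those days.

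**The case against.** The strongest reply is that the trigger is narrow. The nominal interval is 28 days and +7 is a tolerance. An AE that causes the dose due on day 28 to be withheld has already started by then, so it is inside the window and counts. The gap needs a dose already at least 3 days late, then a new AE on days 31-35, then treatment ending before another dose. That is correct and limits the point. It does not remove the point, because the late dose is within the plan's own tolerance and the patient is still on treatment.

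A second reply is that 30 days is a customary tail. As a tail after treatment has ended, that is reasonable. Here the period can expire while the patient is still waiting for a permitted dose.

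A third is that the events remain visible. This is also correct: the listings of discontinuations, SAEs, deaths and non-treatment-emergent AEs would show them, and a study of 60 to 80 patients can be read case by case. But a listed event is in no count or percentage.

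A reader might infer more than the documents support:
- *That 14% of AEs are lost.* That figure is a share of days in a maximally late interval. The documents give no distribution of delays or onset days.
- *That AEs ending treatment in maintenance are generally lost.* Days 0-30 of the interval are covered.
- *That DLT counts are affected.* The DLT period is Days 1-29, before maintenance.
- *That AE collection stops at the End of Study visit, leaving the 30-day window partly unobserved.* The AE rows of the schedules cannot be read reliably, particularly in Table 4, and the protocol's AE reporting section is not in the text available. No conclusion on collection can be drawn.

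**Conclusion.** The point holds in limited form. The TEAE definition and the maintenance tolerance do not fit together, and whether a new AE on days 31-35 enters the tables depends on whether another dose follows. On the routine schedule this is confined to the final, overdue interval before a maintenance dose. The loss is from tables, not from the report. The number of patients affected cannot be estimated and is probably small, but in a Part 2 cohort of about 10 a single event moves a percentage by about 10 points.

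This rests on two assumptions: that the TEAE-only rule also governs the SAE tables whose titles omit the prefix, and that onset dates are known. An AE with a completely missing start date counts, and one missing only the day may be imputed to the first of the month (section 7.3) and so move into the window.

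The change is worth making because it removes outcome-dependent classification from a primary safety summary at almost no cost.

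**What to change.** In SAP section 8.7.2, define the end of the TEAE period as the later of 30 days after the last dose and the date of treatment discontinuation. State that an AE arising while the next dose is pending, or one with the outcome code *drug withdrawn*, is counted. Section 8.6.4 already uses a treatment discontinuation date separate from the last dosing date. The outcome-code clause protects against that date being recorded as the date of the last dose. State also whether the two SAE tables are limited to TEAEs.

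The cost is one line of text and its programming. The downside is that a few more late events, some possibly due to the underlying disease, will count as treatment-emergent.

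Separately, the 28-day limit for the End of Study visit and the maintenance interval of up to 35 days must be reconciled. Which of them should change is for the study team to decide.

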#### 4.1.3.2. Dose Increases

Patients who have completed the consolidation phase of their assigned cohort and have not experienced a DLT, Grade  $\geq 2$  study drug-related injection-site reaction, or required a dose reduction may have their dose escalated to that of the highest cohort for which safety and tolerability have been established. This includes patients from Part 1 of the study having their dose escalated to a Part 2 dose.

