# 8. STATISTICAL ANALYSIS

In this section and all after, when tables are presented by posttreatment visits, the last visit will be the visit at the end of study. When applicable, visits after the start of the maintenance phase and unscheduled visits will be included in a summary of maximum and minimum values observed for each patient's posttreatment visits, i.e., the minimum and maximum values are based on all the post treatment visits.

In general descriptive statistics for continuous variables will be summarized by the mean, standard deviation, 25th percentile, median (50th percentile), 75th percentile, minimum and maximum values. When continuous variables are displayed for less than 3 patients, only the number of observations will be presented. Categorical variables will be summarized using counts and percentages.

All raw data will be presented to the original number of decimal places. The means and medians will be presented to 1 more decimal place than the raw data. The standard deviations will be presented to 2 more decimal places than the raw data.

Baseline will generally be defined as data obtained as the last non-missing value prior to the first dose of study drug, i.e., including the pre-dose assessment on Day 1, assessments during screening and other assessments prior to the first dose of study drug.

AE tables and laboratory tables will be presented by visits and by tumor group. Tumor groups are defined as groups of overall, solid tumor, and AML patients.

Unless otherwise stated, summaries will be produced by dose cohort, which is defined as the intended and starting dose to which the patient was enrolled.

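### The supplementary AE tables by dose received pool patients who started at a level with tolerability-selected patients moved up to it, so their percentages are not comparable across doses

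*SAP*

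**What the plan says.** The main AE tables follow the starting dose. SAP 8.7.2 states: "Tables will present the number and percentage of AEs by starting dose cohort and overall". SAP 8 sets the same default: "summaries will be produced by dose cohort, which is defined as the intended and starting dose to which the patient was enrolled".

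SAP 8.7.2 then adds a second set: "Similar tables will also be presented by the last dose received before the start of the event". For these, "column headers will need to include all patients who were ever dosed at that dose level", and "patients may be counted more than once for each event as the events will be tabled by the last dose level received". Nothing in the section separates the columns by how a patient reached the level or by treatment phase, and no exposure adjustment is given.

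The way up is in SAP 4.1.3.2. It applies to "Patients who have completed the consolidation phase of their assigned cohort and have not experienced a DLT", who have also had no dose reduction and no related injection-site reaction of Grade 2 or higher. Such patients "may have their dose escalated to that of the highest cohort for which safety and tolerability have been established". The section expressly lets Part 1 patients move to Part 2 doses. Under SAP 4.1, dosing after consolidation is every 28 days in both parts. SAP 4.1.3.1 also provides a way down: a patient with a DLT may continue at the next lower level.

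SAP 8.5 summarizes exposure by treatment phase and dose cohort, not by dose level received.

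**The concern.** A table of AE percentages by dose received invites the reader to look along the columns for a dose trend. Here the columns hold different kinds of patient. The escalated group was chosen for having tolerated a lower dose, and one selection criterion, the injection-site reaction, is itself among the AEs tabulated. Escalation goes to the highest established level, so these patients gather in the upper columns, where they receive fewer doses per unit of time than starters did. Patients reduced after a DLT move the other way, into lower columns.

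The starting-dose tables do not repair this. They keep a patient's later events in the starting column, so an AE that follows escalation is credited to the lower starting dose. The exception is 27.0 mg, the highest planned level, from which no escalation is possible.

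At stake is the descriptive reading of AEs by dose, which SAP 6.2 places within the primary safety endpoint. For the AEs most closely tied to dose, a real rise could look flatter than it is.

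**Working it through.** The plan states no AE rate or expected number of escalations, so it has no figure to reproduce. The check uses the schedule and then a mixture calculation with assumed inputs.

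**1. Dosing intensity.** Dose days rebuilt from SAP 4.1 agree with the schedules in SAP 6.1:

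- Part 1: Days 1, 8, 15, 22, 29, 43, 57, 71, 85 (9 doses).
- Part 2: Days 1, 8, 15, 22, 29, 36, 43, 50, 57, 71, 85, 99, 113, 127, 141 (15 doses).
- Escalated patient: one dose every 28 days at the new level.

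| Doses at the level in the first | 28 days | 56 days | 84 days |
|---|---|---|---|
| Part 1 starter | 4 | 6 | 8 |
| Part 2 starter | 4 | 8 | 10 |
| Escalated patient | 1 | 2 | 3 |

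**2. Pooled percentage.** Take 10 starters, the approximate number planned at each Part 2 level (SAP 4.1). Let ps be the starter rate, pe the rate in escalated patients at that level and m their number. The rates and m are assumed.

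Tabulated rate = (10·ps + m·pe) / (10 + m)

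For example, with ps = 40%, pe = 10% and m = 5: (4 + 0.5) / 15 = 30%.

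| pe (ps = 40%) | m = 2 | m = 5 | m = 10 | m = 20 |
|---|---|---|---|---|
| 0% | 33% | 27% | 20% | 13% |
| 10% | 35% | 30% | 25% | 20% |
| 20% | 37% | 33% | 30% | 27% |
| 40% | 40% | 40% | 40% | 40% |
| 60% | 43% | 47% | 50% | 53% |

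The column is diluted when pe is below ps and inflated when pe is above it. With pe = 10% and m = 5, a starter rate of 30% appears as 23% and one of 60% as 43%.

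The effect is smaller at 9.0 mg. With an assumed 30 starters, consistent with up to three RP2D cohorts of 10, the same five patients give (12 + 0.5) / 35 = 36%. Escalated patients can reach that level only from the three lower cohorts of 2 to 6 patients, so at most 3 × 6 = 18 before replacements.

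**3. Direction.** Assume the same 5% risk per dose in both groups. Cumulative risk after k doses is 1 − 0.95^k:

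- 2 doses: 9.8%
- 6 doses: 26.5%
- 15 doses: 53.7%
- 24 doses: 70.8%

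An escalated patient with few doses falls well below a Part 2 starter who completes consolidation (15 doses). It takes 15 monthly doses to match that starter, and more would exceed it. Selection pushes pe down for injection-site reactions in particular, whereas disease-related events can accumulate over a long maintenance period.

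**4. Would splitting the columns be enough?** Group (a), starters followed until any dose change, still has unequal follow-up. A Part 1 starter escalated after consolidation stops at 9 doses, while a Part 2 starter has 15 by the end of consolidation. At the same 5% per dose, that is 1 − 0.95^9 = 37.0% against 53.7%: an apparent dose trend with no dose effect. From Day 1 to just before the fifth dose both parts have the same four scheduled doses, so both give 1 − 0.95^4 = 18.5%. Escalation cannot yet have occurred, because consolidation ends no earlier than dose 9 (Day 85) in Part 1 and dose 15 (Day 141) in Part 2.

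**The case against.** The ever-dosed denominator is coherent: every patient who could contribute an event at a level is counted there, and the SAP discloses the multiple counting. These are supplementary tables, and the dosing and AE listings would let a reader separate the groups. That stands, but listings are not a planned comparison, and a coherent denominator does not make the columns alike.

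Three stronger readings are tempting and are not supported.

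- A reader might infer that MTD determination is compromised. It is not: the MTD rule counts DLTs per cohort over Days 1 to 29, and escalated patients arrive only after consolidation. SAP 6.2 and 8.7.1 also mention the overall safety profile, but attach no rule to it.
- A reader might infer that no planned table shows AEs at the assigned dose free of escalation. At 27.0 mg the starting-dose column does, with only dose reductions left to consider. SAP 8 also says AE tables will be shown by visit, which could separate pre-escalation events. However, the table list in 8.7.2 specifies no such split, and it would not change the by-last-dose denominator.
- A reader might infer that all AE rates at high doses are diluted. The selection argument is strong for injection-site reactions and reasonable for early dose-related AEs. For other TEAEs, open-ended maintenance could push the rate either way.

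The numbers are also small. In the illustration, 4/10 has a Wilson 95% interval of 16.8% to 68.7%, which covers most of the tabulated shifts.

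**Conclusion.** The concern holds as a matter of comparability. In the by-last-dose AE tables, columns that receive escalated patients mix two groups that differ in selection, dosing frequency and time on study, so their percentages should not be read across doses. Dilution is likely for injection-site reactions and early dose-related AEs and uncertain for other TEAEs. Outside 27.0 mg, the starting-dose tables do not fill the gap.

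The size cannot be determined from the documents, because escalation is optional and neither numbers nor rates are given. Under the assumed inputs, 40% among 10 starters appears as 30% with five escalated patients at 10%, and as 25% with ten. It rises to 50% if ten escalated patients have a rate of 60%. The DLT tables and the MTD rule are untouched.

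**What to change.** In SAP 8.7.2, split each dose level in the by-last-dose tables into two groups:

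- (a) patients who started at that level, counting events before any change of dose level;
- (b) patients moved to that level, by escalation or reduction, counting events after the move.

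Give each group its own N and its number of doses or patient-time at the level. In the illustration with 10 starters and 10 escalated patients, the table would show 4/10 (40%) and 1/10 (10%) instead of a single 5/20 (25%, Wilson 95% interval 11.2% to 46.9%).

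For comparisons across dose levels, use group (a) within a common window in which both parts share a schedule and escalation cannot yet have happened, for example Day 1 to just before the fifth dose. Alternatively, report events per dose or per patient-time. State that whole-period group (a) percentages are not to be compared across levels.

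The cost is SAP wording and table shells. The dosing and AE dates are already needed for these tables, and no dosing or escalation rule changes. The downside is more columns with small Ns.
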